## 1.0 Background

Alcohol Use Disorders (AUDs) occur in over 16.6 million adults in the United States and are the leading contributor to premature death and disability among ages 15-49. The estimated economic burden to the United States was \$223.5 billion in 2006. Limiting this damage requires preventing escalation to chronic, treatment-resistant compulsive drinking. AUDs are theorized to progress through 3 overlapping and recurring stages: binge-intoxication, negative affect-withdrawal, and preoccupation-anticipation. Binge-intoxication is initially characterized by impulsive drinking, and a rewarding response to alcohol and the motivation induced by alcohol's associated cues. Repeated alcohol intoxication is thought to lead to negative affect-withdrawal, with a loss of sensitivity to, and eventually withdrawal from, alcohol. Secondary neural adaptations, including an altered stress response, occur, as well. The preoccupation-anticipation stage is thought to be marked by greater executive dysfunction, such as impaired error monitoring and compulsive consumption. By the time drinking has progressed to the more advanced stages of a diagnosed AUD, years of alcohol use have contributed to neuroadaptations in the brain which exacerbate use and make drinking behaviors more *aversion resistant* and difficult to treat. Indeed, latent trait analysis shows that drinking despite adverse interpersonal, psychological, and physical problems is a marker for the most severe stage of AUD severity. Although abstinence does result in some brain recovery, individuals at this advanced stage often have great difficulty maintaining sobriety, in part because of desensitization to adverse consequences.

Drug seeking, self-administration, and aversion resistance during self-administration are defining behaviors of preclinical models of addiction. The animals' behaviors vary according to their history of alcohol exposure. In contrast, aversion resistant drinking in humans is either established by self-report or clinical inference, without objective behavioral quantification, complicating our understanding of its relationship to lifetime drinking history. Further, the use of *quantified* lifetime drinking history as an independent variable has largely been limited to epidemiologic rather than experimental studies. Consequently, human research has failed to examine how lifetime drinking history contributes to behavioral alcohol seeking and disease progression.

There is an unfulfilled need to develop an objective measure of human ARD. Such a measure would illuminate mechanisms of disease progression and advance the translation between clinical, human laboratory, and preclinical work. "Self-report" is clearly insufficient, requiring insight, accurate perception of consequences, and willingness to report. Most individuals, even those without an AUD, minimize reporting their drinking and its consequences. Thus, many affected individuals are not identified until symptoms are severe enough to be recognized by friends, family, co-workers, or the courts. In contrast to self-report, we posit that measured alcohol "seeking despite aversion" (SDA) reflects AUD progression. We assert that SDA emerges early, progresses with lifetime drinking, presages the onset of aversion and treatment-resistant drinking and AUD diagnosis, is associated with decreased sensitivity to alcohol, and reflects AUD risk and severity.

Only a multidimensional understanding of AUD will lead to more effective treatment approaches that integrate social, behavioral, and biological aspects. This project will advance both basic research and clinical knowledge by embracing multidimensionality. Development of novel, objective measures of SDA characterizing early AUD progression is an important research tool. In basic research, it could help to understand the brain circuits involved in the transition to compulsive drinking. In clinical research, SDA would be a prime tool for testing pharmacologic and behavioral treatments. Current treatment approaches require people to self-report changes

in drinking, craving, and withdrawal symptoms, requiring both insight and objectivity. Identifying the mechanisms and neuroadaptations underlying early stages of AUD progression will lead to an integrated view of addiction across genetic, brain, behavioral, and social levels of analysis.

Our project will build on substantial evidence from the literature that supports the notion that neural adaptations from excessive and extended drinking yield aversion and treatment-resistant drinking behaviors. This project focuses on a problem with a large clinical health impact. It seeks to fill an important gap in how we assess staging of human AUDs in both basic research and clinical research. We propose a multiple level of analysis approach, consistent with the Research Domain Criteria mission and the goals of the Indiana Alcohol Research Center (IARC). Our pilot data strongly support the feasibility of this approach and viability of the proposed hypotheses.

## 2.0 Rationale and Specific Aims

Prolonged alcohol use results in neuroadaptations. The consequences include a decreased sensitivity to alcohol, a shift from positive to negative reinforcement-based alcohol use, increased negative affect that drives further consumption, and ultimately, aversion-resistant drinking (ARD; drinking despite resultant problems and adverse consequences). ARD is a hallmark of more severe and treatment-resistant compulsive use and is modeled well in preclinical research. There are, however, no well-validated models of human ARD and, little understanding of the neural signature underlying the transition to ARD. This project seeks to validate such a model and to examine its principal determinants in 100 subjects.

The development of ARD marks an important transition from treatment-sensitive to treatment-resistant drinking behaviors. This creates a critical need to develop an objective measure of ARD in humans and to characterize its neural functional substrates. We propose that alcohol seeking despite aversion (SDA) is an early marker of ARD in humans, attributable to the neuroadaptations caused by excessive exposure to alcohol. An objective measure of SDA in human alcohol use will lead to better understanding of the mechanisms of disease progression in humans and advance the translation between human and animal work.

Our long-term goal is to use SDA as a platform for the laboratory testing of novel pharmacologic and behavioral interventions that can be used among those with the highest risk, but who have yet to progress to treatment-resistant drinking. The objective of this project is to test SDA across multiple levels of analysis. We consider SDA as an early marker of alcohol use disorder progression that is related to lifetime drinking history, alcohol use disorder risks, and brain physiology. Our current IARC pilot study (IRB #) demonstrates that SDA can be objectively quantified via an intravenous alcohol self-administration task, where operant work for identical incremental alcohol rewards is paired with aversive stimuli. Our preliminary data support our central hypothesis: that behavior in the SDA model is attributable to lifetime alcohol exposure, is related to alcohol use disorder (AUD) risk factors and phenotypes, and reflects alterations in neural system function. Specifically, they suggest that the degree of SDA is positively associated with recent drinking history, negative affect-based rash action (i.e. negative urgency, including action with respect to alcohol use), and self-rating of the effects of alcohol. The rationale for this work is that it would lead to the first objective, well-validated measure of SDA in humans.

Our specific aims are to:

*Aim 1:* Characterize SDA as a function of lifetime drinking history.

*Hypothesis 1:* Greater SDA will reflect greater lifetime drinking history.

*Hypothesis 2:* Those with a high lifetime drinking history will demonstrate less sensitivity to aversion in the preference to work for alcohol. Specifically, those with a high lifetime drinking history will work more for alcohol compared to water under both aversive and neutral experimental conditions, whereas those with a low lifetime drinking history will only work more for alcohol compared to water when alcohol seeking is paired with neutral stimuli.

Aim 2: Quantify associations between SDA and alcohol use disorder severity, and between SDA and risk phenotypes; then characterize how these risk factors classify individuals into those who will and will not work for alcohol in the context of aversive stimuli.

*Hypothesis 3:* Those with greater SDA will have greater AUD severity, greater negative urgency, a greater density of familial alcoholism, and reduced subjective, behavioral, and electrophysiologic sensitivity to alcohol.

*Hypothesis 4:* Significant factors from hypothesis 3 will identify a latent trait that classifies individuals into two types: those who have high SDA and those who have low SDA.

Aim 3: Identify signatures of neural function that underlie SDA.

*Hypothesis 5:* Those with greater SDA will demonstrate reduced event-related potential component amplitudes differences between negative vs. positive feedback about per-trial progress toward a reward. Those with greater SDA will demonstrate

*Hypothesis 6a:* greater resting state crosstalk between the default mode and fronto-parietal networks and *Hypothesis 6b:* reduced ventral striatal-ventromedial frontal connectivity.

The positive impact of this project will be to advance the translation between preclinical and clinical models and to elucidate distinct mechanisms underlying AUD progression in humans. Importantly, the proposed model uses objective behavior, rather than subjective symptom report. Our human component project is centered on the IARC theme and complements its preclinical components and methodologies. We expect that the results will facilitate the identification and evaluation of pharmacologic and behavioral interventions to minimize the risk of AUD progression risk in drinkers who have yet to manifest treatment resistant behavior.

### 3.0 Inclusion/Exclusion Criteria

#### Inclusion

- Overtly healthy men and women aged 21 – 55
- Either 25-50 kg or 250-500 kg Lifetime Drinking History (LDH) and recent drinking of at least 7 drinks/week for women and 10 drinks/week men, or any recent drinking or LDH below 500 kg at the discretion of the PI.
- Able to understand/complete questionnaires and procedures in English
- Have venous access sufficient to allow blood sampling

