#### 4.0 Enrollment/Randomization

The project employs a between-participants design. Each participant will undertake 3 or 4 sessions: an interview/screening session, 2 randomly counter-balanced (neutral and aversive stimuli) IV alcohol self-administration sessions, and in a subset of subjects that meet the criteria outlined in the fMRI screen, an fMRI resting state scan. All sessions will take place in the Neural Systems Laboratory at the Indiana Clinical Research Center at Indiana University Hospital or at the Neuroscience Center at Methodist Hospital.

We will consent 300 participants to enroll 150 and complete 100 participants: **a**) 50 individuals who are current drinkers with lower lifetime drinking history, between 25-50 kg ethanol, **b**) 50 individuals who are heavy drinkers with a higher lifetime drinking history of 250-500 kg ethanol, and **c**) individuals below 500 kg ethanol at the discretion of the principle investigator. We will target equal numbers of men and women for inclusion in the lower and higher lifetime drinking groups. Total participant payment will be \$400, plus parking/travel costs.

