## **7.0 Statistical Considerations**

### **Aim 1: Characterize SDA across lifetime drinking history.**

#### Aim 1 Hypothesis Testing Plan

[figure not shown]
*Hypothesis 1: Greater SDA will reflect greater lifetime drinking.* We will conduct a linear mixed-model analysis, with lifetime drinking history as the continuous independent variable and with SDA as the dependent variable. Lifetime drinking history will be defined as the kg of alcohol reported consumed via the Concordia Lifetime Drinking Questionnaire. SDA will be defined as the amount of work performed (cumulative number of SDA trials completed) for alcohol rewards in the aversive session. Age, gender, recent drinking history, and race will be included as covariates, due to their relationship with AUDs.

**Hypothesis 2:** Those with a high lifetime drinking history will demonstrate less sensitivity to aversion in the preference to work for alcohol. Specifically, those with a high lifetime drinking history will work more for alcohol compared to water under both neutral and aversive conditions, whereas those with a low lifetime drinking history will only work more for alcohol compared to water in the neutral session. We will conduct a mixed linear model in which lifetime drinking history is the independent variable, as in hypothesis 1, but using a different dependent measure. We will subtract work for water from work for alcohol, dividing the difference by the sum of the work done for alcohol plus water (separately under the aversive stimulus ( $R_a$ ) and under the neutral stimulus ( $R_n$ )). The ratios  $R_a$  and  $R_n$  will be used as the repeated measures dependent variables, and lifetime drinking history (high vs. low), stimulus type (aversive vs. neutral) and their interaction will be independent variables. Covariates will include age, gender, recent drinking history, and race. If lifetime drinking history and the interaction with stimulus are significant predictors of the ratios of work performed, we will conduct follow-up planned contrasts to examine the ratios separately for the neutral and aversive sessions to test high and low lifetime drinking history.

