### Power Analyses

Alcohol self-administration: Our previous alcohol self-administration work showed effect sizes from 0.49 to 1.31 according to the phenotype of interest. Neurophysiological correlates (EEG/fMRI): Published outcome and feedback-related differences in N200 and P300 amplitudes yield effect sizes from 0.78 to 2.12 for subjects with an AUD versus controls, and 0.62 to 1.6 for the effect of alcohol. There are no standards for power analyses in whole brain connectomics. However, our pilot data showed significant results in  $n=51$ , suggesting  $n=100$  is sufficient to find robust connectivity patterns. We will ensure robustness using permutation tests combined with an extent threshold, or alternatively, using the Permutation Network Framework. Relationship to AUD risk variables: In our pilot data, the relationship between SDA and AUD risk correlates ranged from  $r=0.32 - 0.63$ . With a sample of  $n=100$ , we can detect an effect size of at least 0.32 and still maintain adequate  $power=0.90$ ,  $\alpha=0.01$ . When categorized by groups of  $n=50$  (high/low lifetime drinking history), we can detect differences with an effect size of 0.64 and still maintain adequate  $power=0.90$ ,  $\alpha=0.01$ .

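### Power for the lifetime drinking history (LDH) contrast is stated without covariates, but H1 and H2 test LDH adjusted for age and recent drinking, which are likely to overlap strongly with it

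*Combined protocol and SAP*

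**What the plan says.** Section 3.0 (Inclusion) admits ages 21 to 55 with "Either 25-50 kg or 250-500 kg Lifetime Drinking History (LDH) and recent drinking of at least 7 drinks/week for women and 10 drinks/week men". The same sentence then lets the PI accept any recent drinking, or any LDH below 500 kg. Section 4.0 plans "50 individuals who are current drinkers with lower lifetime drinking history, between 25-50 kg ethanol" and "50 individuals who are heavy drinkers with a higher lifetime drinking history of 250-500 kg ethanol", plus a third, discretionary group below 500 kg. The only balance rule is on sex: "We will target equal numbers of men and women for inclusion in the lower and higher lifetime drinking groups". No age quota, matching or stratification appears.

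For Hypothesis 1, with LDH continuous, the Aim 1 plan states: "Age, gender, recent drinking history, and race will be included as covariates, due to their relationship with AUDs". Hypothesis 2 uses the same four covariates, with LDH as high versus low, stimulus type and their interaction. Its follow-up contrasts are run only if both LDH and the interaction are significant.

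The Power Analyses section says that with n = 100 "we can detect an effect size of at least 0.32 and still maintain adequate" power of 0.90 at alpha 0.01, and that with 50 per group "we can detect differences with an effect size of 0.64 and still maintain adequate" the same power at the same alpha. It mentions neither covariates nor sidedness.

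**The concern.** LDH is in essence years of drinking multiplied by average rate. Age stands close to the first factor and recent drinking to the second, so a model containing both leaves LDH only the variation they do not explain. The standard error of the LDH coefficient grows by 1/sqrt(1 - R²), where R² is the share of LDH variance explained by the covariates. The power section makes no allowance for this.

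Aim 1 rests on this term. If power is much lower than stated, a null result says little. If the LDH groups overlap poorly in age, a positive result leans on a linear age term to separate lifetime exposure from ageing where few participants of the same age can be compared.

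**Working it through.** **Inputs from the documents.** 50 completers per group (section 4.0; "We will consent 300 participants to enroll 150 and complete 100 participants"); d = 0.64, r = 0.32, power 0.90 and alpha 0.01 (Power Analyses); covariates age, gender, recent drinking and race (Aim 1 plan).

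**Inputs not in the documents (assumed).** 14 g ethanol per drink; onset of drinking at about 16 to 17; the spread of drinking rates; hence R².

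**Step 1. Reproduce the stated figures, no covariates.**
- Two groups: noncentrality = d × sqrt(n/2) = 0.64 × sqrt(25) = 3.20. Power (noncentral t) is 0.89 at two-sided 0.05, 0.72 at two-sided 0.01 and 0.80 at one-sided 0.01.
- Correlation: atanh(0.32) × sqrt(97) = 0.332 × 9.85 = 3.27. Power is 0.90 at two-sided 0.05, 0.755 at two-sided 0.01 and 0.83 at one-sided 0.01.

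The stated 0.90 is matched, or nearly so, at two-sided 0.05 but not at the stated 0.01. Both calculations are unadjusted.

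**Step 2. Why the groups tend to differ in age.** kg per year = drinks/week × 52 × 14/1000.
- At the entry minimum: 7/week gives 5.10 kg/year and 10/week gives 7.28. Passing 50 kg takes 50/5.10 = 9.8 or 50/7.28 = 6.9 years. Reaching 250 kg takes 49 or 34 years.
- At 20/week (14.56 kg/year) 250 kg takes 17 years; at 30/week (21.84) it takes 11.
- With onset at 16, a 40-year-old in the low band averaged at most 50,000/(24 × 52 × 14) = 2.9 drinks/week, below the current minimum. A 25-year-old in the high band averaged at least 250,000/(9 × 52 × 14) = 38.

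**Step 3. Plausible R².** Simulated histories used 14 g per drink, onset about 17, lognormal lifetime rates with median factor 6 or 10 drinks/week, log-SD of recent versus lifetime rate 0.2 to 1.2, and uniform or young-skewed ages.
- Weekly minimum enforced: mean age 23–30 (low) versus 37–45 (high), age-distribution overlap 5–37%, R² of LDH group on age, sex and recent drinking 0.54–0.90.
- Weekly minimum waived, bands kept: mean age 27–34 versus 37–45, overlap 37–49%, R² 0.52–0.81.
- Other assumed histories gave R² of about 0.5–0.85 (enforced) and 0.34–0.85 (waived).

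I take 0.35 to 0.85 as a working range.

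**Step 4. Power for the adjusted LDH term.** Noncentrality = 0.64 × sqrt(25 × (1 - R²)), df = 93, two-sided, with 0.64 read as the adjusted difference in residual SD units. Detectable d is the unadjusted value (0.655 at alpha 0.05, 0.786 at 0.01) divided by sqrt(1 - R²).

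| R² | Noncentrality | Power, alpha 0.05 | Power, alpha 0.01 | d at 90% power, 0.05 / 0.01 |
|---|---|---|---|---|
| 0 | 3.20 | 0.89 | 0.72 | 0.66 / 0.79 |
| 0.3 | 2.68 | 0.76 | 0.52 | 0.78 / 0.94 |
| 0.5 | 2.26 | 0.61 | 0.36 | 0.93 / 1.11 |
| 0.7 | 1.75 | 0.41 | 0.20 | 1.20 / 1.43 |

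At the ends of the working range, power is 0.72 / 0.48 (R² 0.35) and 0.23 / 0.09 (R² 0.85).

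**Step 5. Offset from outcome variance explained.** If the covariates also explain 30% of outcome variance (assumed), noncentrality is divided by sqrt(0.7). At R² = 0.5 it becomes 2.26/0.837 = 2.70, and power is 0.76 / 0.53.

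**Step 6. Which tests are affected.** The factor applies to H1 (simulated R² for continuous LDH in a two-band sample was 0.51–0.90) and to the between-person LDH main effect in H2. The LDH-by-stimulus interaction compares each person's aversive and neutral ratios. Covariates entered as main effects cancel from that difference, so it carries no such penalty.

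**The case against.** The strongest objections, and what of each stands:

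- **The entry rule is not rigid.** A reader of the bands and minimum alone might infer that the design compares two age groups and that adjustment removes most of the LDH contrast. The documents do not support that. The PI may waive the minimum and admit intermediate LDH values, which H1 can use, and no age distribution by group is given. The age difference is a tendency. Still, a discretionary waiver sets no age balance, and simulated R² stayed substantial with the minimum waived.
- **The size rests on assumptions.** Drink size, onset age and stability of drinking are not in the documents, and the minimum concerns recent rather than lifetime drinking. This stands, so only a range can be given.
- **The gap to 0.90 has another cause.** It is tempting to blame the whole shortfall on covariates. At the stated alpha, power is 0.72 (two-sided) before any adjustment. That is a separate error.
- **The H2 interaction escapes.** Correct; a reader might extend the precision loss to all of H2, but that would be wrong. The interaction has a different weakness: no age-by-stimulus term is planned, so an age difference in response to aversive stimuli could appear as an LDH effect. The main effect also gates the H2 contrasts, so its low power still matters.
- **Covariates reduce residual variance too.** True; section 2.0 reports a pilot association of seeking despite aversion (SDA) with recent drinking. Step 5 shows that explaining 30% of outcome variance recovers part of the loss.
- **The power section does not claim to describe adjusted models.** True, but it offers no other figure for H1 or H2.

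**Conclusion.** The point holds as one about the stated power and its interpretation. The plan tests LDH adjusted for two variables close to its components, sets no age balance, and gives power only for unadjusted comparisons. For d = 0.64 with 50 per group, an R² of 0.5 lowers power from 0.89 to 0.61 at two-sided 0.05 and from 0.72 to 0.36 at two-sided 0.01. Even a mild R² of 0.3 gives 0.76 and 0.52. These powers follow from the formula; where the trial falls within roughly 0.35 to 0.85 depends on assumed drinking histories and should be settled from observed data where possible. The loss concerns H1 and the H2 LDH main effect. For the H2 interaction the issue is possible age confounding. The documents do not show that the groups fail to overlap in age, nor that an LDH effect independent of age cannot be estimated.

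**What to change.** 1. In Power Analyses, restate detectable effect and power for the covariate-adjusted LDH term in H1 and the H2 main effect. Give alpha and sidedness, and show results over a range of R² of LDH on the covariates, taken from enrolled participants if data exist.
2. In the Aim 1 plan, prespecify as a sensitivity analysis H1 and H2 within the age range that both LDH groups occupy, with age modelled flexibly. Add an age-by-stimulus term to H2. Report age by LDH group, and qualify any claim of an LDH effect independent of age if overlap is poor.

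Both are wording changes to the analysis plan. The cost is a less favourable power figure and an overlap analysis that is smaller, less precise and possibly made up of atypical drinkers, which is why it should not carry the main claim. An age-band recruitment target is optional: it could improve overlap but may be hard to fill, and the point does not depend on it.
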